Enrolled patients and their families will be randomized 1:1 after discharge to the intervention group or standard-of-care using a permuted block randomization stratified by home state of residence (Ohio vs. Kentucky) to ensure equal allocation of the intervention within each stratification block. Random permutations within each block within each stratum will be generated using a random number generator available in SAS Proc Plan. The use of randomization in the study design is crucial for avoiding bias in the evaluation of the effectiveness of the nurse phone call intervention. Patients and families cannot be blinded given that the nature of the intervention is a nurse phone call. However, we will attempt to mitigate the potential bias in the following manner: 1) Families will be asked to refrain from disclosing intervention status to the interviewer at the follow-up phone call; and 2) Study staff will be blinded to treatment assignment when making the follow-up phone call. Study staff will use a written script to administer the survey. At the start of the call, families will be reminded to refrain from disclosing their intervention status.

Post-Hoc Analysis

Qualitative Analysis: The post-hoc analysis of this proposal will use qualitative methods, specifically interviews and focus groups. At the completion of the post-hoc analysis, we will have an improved understanding of the experiences, challenges, and successes of pediatric inpatient-to-outpatient transitions from the perspective of families and providers. Qualitative methods are the best means to generate consensus themes about patient and family experiences and preferences during inpatient-to-outpatient transitions. Interviews will be used to gain insight into what families and providers believe to be both the most relevant barriers to successful transition and the outcomes they find to be most meaningful. Participants will respond to semi-structured interviews and focus groups. The interviewer will use follow-up probes to expand and clarify responses and further elucidate the context of the responses. This qualitative methods process will permit us to gain unique perspectives and understand more deeply our results.

Readmission Analysis:

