parents or caregivers will be able to attend the focus groups given their demanding schedules, childcare priorities, and transportation barriers. Thus, we will seek to recruit 10-12 participants per group to account for the possibility of participants failing to show up as scheduled. Recruitment will take place on the hospital wards during a child's admission. We anticipate it will take approximately 2 months to recruit the 120-160 participants necessary to ensure that we have 90-110 for our focus group sample. We expect that we will reach thematic saturation by the conclusion of these groups, meaning no new ideas or themes will be generated at that point and recruitment will be suspended.

Aim 2

Eligible patients and families will be identified by frontline clinical providers, with no input from the research team. We believe that up to 600 families will participate in this Aim. Clinical research coordinators will contact all of the families that participate in this aim via phone to participate in a short follow-up call.

Clinical research coordinators will also identify up to 100 patients during this Aim that receive primary care at one of the three CCHMC primary care clinics (Pediatric Primary Care Center, Hopple Street Clinic, and Fairfield Primary Care). We will review the patient's chart to assess return visits to primary care 30-days after admission, then will call the families to confirm their recall of these visits.

For the phone call optimization, we believe that up to 150 families will participate in this Aim. These families will receive the nurse phone call within 96 hours of discharge, then will receive a phone call from a clinical research coordinator 1-7 days after the visit to complete a short phone call about their experience with the call and any feedback they may have to improve the call.

Aim 3

All patients and families that meet the above inclusion and exclusion criteria will be eligible for the study, and will be approached, depending on CRC schedule. We anticipate enrolling up to 2000 families during this aim. We will conduct planned HET analyses.

Aim 4

All patients and families that meet the above inclusion and exclusion criteria will be eligible for the study, and will be approached, depending on CRC schedule. We anticipate enrolling up to 2000 families during this aim.

Post-Hoc Analysis

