We have multiple planned analyses to examine potential heterogeneity of treatment effect of the nurse visit. Factors included in the HET analysis are insurance, primary care access, financial strain, caregiver education, hospital service, and medical complexity. Medical complexity will be determined by the pediatric medical complexity algorithm (PMCA). The PMCA is a publicly available algorithm that identifies children with complex chronic disease (who have accessed tertiary hospital care). The algorithm includes three levels of medical complexity: children with complex chronic disease (C-CD), children with non-complex chronic disease (NC-CD), and children without chronic disease (CD). In order to calculate the PMCA we will collect additional administrative data for all patients enrolled in Aims 3 and 4. This data will include: ICD9 Codes/ICD10 codes, procedure codes, admission date, discharge dates, admitting and discharge departments. We will capture all outpatient, urgent care, ED, and hospital events within the specified time window (February 1, 2012 to April 30, 2016). The PMCA will be calculated based on a 3-year window before the index hospitalization.

Aim 4

Analyses: For the primary outcome, the dependent variable will be a dichotomized indicator of any occurrence of healthcare reutilization within 30 days of hospital discharge. Differences between phone intervention and control groups on this outcome will be evaluated using logistic regression with census tract poverty and discharge service unit included in the model. Other potential covariates (e.g. baseline characteristics with large differences between groups) will be included in a secondary analysis model evaluating the effectiveness of the phone intervention. For secondary outcomes, PDCS total score and number of days back to normal routine perceived by the caregiver at 14-day post-discharge will be analyzed as continuous variables. Differences between the phone intervention and control groups will be evaluated using linear regression with census tract poverty and discharge service unit and other potential covariates included in the model.

Sample size: Assuming a 20% reutilization rate in the control group, a sample size of 750 in the control group and 450 in the phone intervention group will achieve 80% power to detect a 7.1% decrease in reutilization rate (12.9% event rate) for the phone call intervention group with alpha=0.05, allowing for 11% noncompliance.

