For our secondary outcomes, allowing for 11% noncompliance and 5% attrition, the sample size will achieve 80% power to detect a mean difference of 3.1 points on the PDCS between control and phone intervention groups assuming a standard deviation of 16 points for both groups. The sample size will achieve 80% power to detect a mean difference of 0.98 days for return to normal routine assuming a standard deviation of 5 days for both groups. Both estimates assume alpha 0.05 and a 2-sided test.

Post-Hoc Analysis

Qualitative Analysis:

The team will meet to discuss the interviews and identify ideas, concepts, and themes of the interviews. Weekly meetings will be held until the completion of the interviews allowing for ongoing scrutiny and feedback about the interpretation of the data. Interview and focus group transcripts will be de-identified and reviewed by investigators and lead CRC trained in qualitative data analysis. The investigators and lead CRC will meet on a regular basis to discuss the transcripts, and will define and organize themes in an iterative fashion. The results of these interviews and focus groups will provide a deeper understanding of our results.

Readmission Analysis:

We will compare the percentage of readmissions designated as potentially preventable in those patients randomized to the intervention in Aim 3 compared to the percentage of readmissions designates as potentially preventable in those patients randomized to the control group in Aim 3

FACILITIES AND PERFORMANCE SITES

All research activity will occur within the CCHMC Burnet Campus and Liberty Campus inpatient wards. Other CCHMC sites such as College Hill Campus will not be included.

POTENTIAL BENEFITS

The potential benefits of the proposed research are to improve the nurse home visit and phone call program and inpatient to outpatient transitions experiences for families, nurses, and PCPs. Subjects receiving home visits or phone calls could potentially benefit directly from this intervention. Additionally, information obtained from the research findings may benefit other families in the future. The risk of loss of confidentiality is reasonable in relation to the anticipated benefits to the subjects, especially with the appropriate precautions noted.

POTENTIAL RISKS, DISCOMFORTS, INCONVENIENCES AND PRECAUTIONS

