Official Title: Supplement to Hospital to Home Outcomes (H2O): A Study to Improve the Fluidity of Transitions Between Hospital and Home

NCT: 03224130

Date: 20 September 2018

H2O Statistical Analysis Plan for Supplement (AIM 4)

Prepared by:

[name]

[name]

Date:

11/3/2016

Analysis plan approved by:

[name], MSCE

Professor, Division Director

Division of Hospital Medicine

PI H2O

The results of H2O Supplement (Aim 4) will be assessed as described in this document. This statistical analysis plan begins with an overview of the key components of the study including its design, objectives, and outcome measures. This is followed by a detailed description of the statistical analyses that will be utilized to address H2O Supplement Grant Aim 2 study hypotheses.

- 1. Overview of study: This study is single center, parallel, randomized trial to evaluate the effectiveness of a nurse phone call. Patients that meet eligibility criteria will be randomized 1:1 to receive either the intervention group (a nurse phone call within 96 hours of discharge) or the control group (standard-of-care). The randomization scheme utilized permuted block with two stratification factors, SES and state, to ensure equal allocation of the intervention within each stratification block. Random permutations within each block within each stratum were generated using a random number generator available in SAS Proc Plan. The planned enrollment is a total of 900 patients with enrollment ending October 31, 2016.
- **1.1 Study Objective**: To evaluate the effectiveness of a nurse-led telephone intervention for families following their child's hospitalization for acute illness.

Working hypothesis 1: Patients who receive the nurse phone call will have a significantly lower occurrence of any unplanned re-hospitalization and/or any emergency/urgent care visits within 30 days of hospital discharge compared to the patients enrolled in the standard-of-care group.

Working hypothesis 2: Patients who receive the nurse phone call will have significantly better post discharge coping difficulty scores and faster return to normalcy compared to patients in the standard-of-care group.

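### Aim 4 power is calculated for 750 controls and 450 phone patients, but the trial randomises 1:1 and the SAP plans 900; at 450 per arm, power is about 72%, not 80%, on the reading that reproduces the protocol's figure

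*Protocol*

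**What the plan says.** **Power basis.** The protocol (DATA ANALYSIS/METHODS, Aim 4, Sample size) assumes a 20% control rate and states that "a sample size of 750 in the control group and 450 in the phone intervention group will achieve 80% power" for a 7.1-point decrease, with alpha 0.05 and an 11% noncompliance allowance. The secondary-outcome statements that follow rest on the same sample, with 5% attrition added: "the sample size will achieve 80% power to detect a mean difference of 3.1 points on the PDCS" (SD 16) and "The sample size will achieve 80% power to detect a mean difference of 0.98 days for return to normal routine" (SD 5). It then adds: "Both estimates assume alpha 0.05 and a 2-sided test". That sentence covers the two secondary estimates. Sidedness is not given for the primary outcome.

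**Allocation.** The protocol (STUDY DESIGN, Aim 4) has patients "randomized 1:1 after discharge to the intervention group or standard-of-care using a permuted block randomization stratified by home state of residence". SAP section 1 agrees: "Patients that meet eligibility criteria will be randomized 1:1 to receive either the intervention group".

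**Total.** SAP section 1: "The planned enrollment is a total of 900 patients with enrollment ending October 31, 2016". The protocol's recruitment section for Aim 4 gives only an upper limit: "We anticipate enrolling up to 2000 families during this aim".

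**Possible source of extra controls.** SAP section 2.3.2 compares the trial's own intervention and control groups. Parent-study controls appear only in the exploratory four-arm model of SAP sections 1.7 and 2.4. There they form a separate arm, and the model is run only if the funder asks for it. The SAP has no power calculation; its sample-size item in section 2.3.1 lists counts to report.

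**The concern.** A 5:3 split cannot come from 1:1 permuted blocks, so the power paragraph conflicts with the allocation whatever total governs. If the SAP's 900 governs, the phone arm matches (900 / 2 = 450), but the control arm is 750 - 450 = 300 patients short of what was assumed.

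These are the only power statements for Aim 4, and they cover the primary outcome and two secondary outcomes. Anyone who interprets a null Aim 4 result by the stated 80% and the stated detectable differences is relying on a larger trial than the SAP describes. Type I error, the analysis model and the estimates are not affected.

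**Working it through.** **Inputs.** Control rate 0.20, decrease 0.071, alpha 0.05, 11% noncompliance, 5% attrition (secondary outcomes only), SDs 16 and 5, arms 750 and 450: all from the protocol's Aim 4 sample-size text. 1:1 allocation comes from both documents, and the total of 900 from SAP section 1. Two assumptions are needed for the primary outcome because the text does not settle them: the test is two-sided, and noncompliance dilutes the effect.

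**Primary outcome.** The diluted phone rate is 0.20 - 0.89 × 0.071 = 0.1368, a difference of 0.0632. For the two-proportion test,

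power = Φ[(0.0632 - 1.96 × SE0) / SE1],

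where SE0 uses the pooled rate and SE1 the two separate rates. The detectable decrease d solves the same equation at 80% power with phone rate 0.20 - 0.89d.

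| Control / phone | SE0 | SE1 | z | Power for 7.1 points | Decrease detectable at 80% |
|---|---|---|---|---|---|
| 750 / 450 (protocol) | 0.02272 | 0.02181 | 0.855 | 80.4% | 7.07 points |
| 450 / 450 (SAP total, 1:1) | 0.02495 | 0.02486 | 0.575 | 71.7% | 7.8 points |
| 600 / 600 (1,200, 1:1) | 0.02161 | 0.02153 | 0.968 | 83.4% | 6.8 points |
| 1000 / 1000 (upper limit, 1:1) | 0.01674 | 0.01668 | 1.822 | 96.6% | not needed |

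The first row reproduces the stated 80% and 7.1 points. The third shows that equal allocation of the same 1,200 patients would raise power, so the shortfall is due to the 300 absent controls.

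**Other readings.**

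| Reading | 750 / 450 | 450 / 450 |
|---|---|---|
| Noncompliance as 11% loss of sample | 85.5% | about 77% |
| Noncompliance ignored | 89.3% | 82.0% |
| Dilution, one-sided alpha | 88.2% | 81.4% |

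None of these reproduces 80% at 750 and 450. In every one, moving to 450 per arm costs roughly 7 to 8 percentage points; under two-sided dilution it costs 80.4 - 71.7 = 8.7. Changing the test (unpooled variance, continuity correction, log-odds, arcsine) while keeping two-sided dilution gives 78.0% to 82.6% at 750 and 450, and about 69% to 72% at 450 per arm.

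**Secondary outcomes.** Detectable difference = (1.96 + 0.842) × SD × √[1/(0.95 n1) + 1/(0.95 n2)] / 0.89.

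- 750 / 450: 3.08 PDCS points (stated 3.1) and 0.96 days (stated 0.98, so close but not exact).
- 450 / 450: 3.44 points and 1.08 days.
- 600 / 600: 2.98 points and 0.93 days.

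Because the days figure is not exactly reproduced, the stated values can instead be scaled by the ratio of standard errors, which does not depend on the noncompliance rule. At 450 per arm the factor is √[(2/450) / (1/750 + 1/450)] = √1.25 = 1.118, giving 3.1 × 1.118 = 3.47 points and 0.98 × 1.118 = 1.10 days. At 600 per arm it is √0.9375 = 0.968, giving 3.00 points and 0.95 days.

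**The case against.** The strongest reply accepts the mismatch and disputes the 72%.

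- **It depends on conditions the text does not settle.** 900 must govern, noncompliance must be dilution, and the test must be two-sided. With noncompliance ignored or one-sided alpha, 450 per arm still exceeds 80%; a 1:1 trial of 1,200 does too, and the upper limit of 2,000 allows one. This stands as a caution. But the two readings that stay above 80% at 450 per arm give 88% to 89% at 750 and 450, so they are not the protocol's calculation. 900 is also the only planned Aim 4 total outside the power paragraph.
- **The secondary-outcome rule is not fully identified.** This stands: 0.96 is not 0.98. That is why ranges are given.
- **The 20% control rate may not fit Aim 4.** For Aim 3 the protocol builds it as 0.9 × 5% + 0.1 × 15% + 10% + 4% = 20%. The SAP's Aim 4 outcome does not name unscheduled follow-up, and Aim 4 does not recruit from the surgical service. Without those components the sum would be about 15% to 16%, though how much of the 4% is urgent care is not stated. From 16%, at 450 per arm with dilution, a 7.1-point drop would have 81% power, but the same relative reduction (7.1 / 20 = 35.5%) only about 60%. The rate should therefore be confirmed when power is restated. This does not repair the arm sizes.
- **The fix cannot change recruitment.** The SAP is dated 11/3/2016, after the enrolment end that it gives, and a null result can be judged by its confidence interval. True, but a stated power that the design does not deliver should still be corrected.

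The 750 may have been meant to include parent-study controls, or may be left over from another design; the protocol's Aim 4 model adjusts for discharge service unit where the SAP's adjusts for state. The documents do not say. If parent-study controls were meant, the power statement describes something other than the randomised primary comparison.

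**Conclusion.** The concern holds. The Aim 4 power statements describe 750 and 450 patients, which matches neither the 1:1 allocation in both documents nor the SAP's total of 900. This is an inconsistency between passages, not a miscalculation. If 900 governs, and with a 20% control rate, a two-sided test and noncompliance as dilution, power for a 7.1-point decrease is about 72%. A true effect of that size would be missed about 28% of the time instead of 20%. If 1,200 governs at 1:1, power is about 83%; the statement is then conservative but still describes the wrong arms. Confidence is high in the mismatch and in the direction of the loss at 900. The exact 72% is only as firm as those assumptions.

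**What to change.** 1. Agree the Aim 4 total and allocation across the protocol's design and sample-size sections and SAP section 1, and say where the 750 came from.
2. Restate power and detectable differences for the primary and both secondary outcomes under that design. If 900 is the total: about 72% power for 7.1 points, and 80% power for about 7.8 points (20% to 12.2%), 3.4 to 3.5 PDCS points and 1.08 to 1.10 days. If 1,200 is the total: 600 per arm, about 83% power for 7.1 points, and 80% power for 6.8 points, about 3.0 PDCS points and 0.93 to 0.95 days.
3. State that alpha is two-sided for the primary outcome, how the 11% noncompliance was applied, and that 20% is the expected control rate for the Aim 4 outcome as the SAP defines it. If any of these differs from what is assumed here, recompute with the rule or rate actually used.

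The cost is wording in the Aim 4 sample-size paragraphs and one agreed total. No extra enrolment is proposed, and the upper limit of 2,000 need not change. If 900 is confirmed, the stated power and detectable differences will look less favourable.

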methods will be used to adapt the current processes to ensure that the visit and phone call addresses barriers reported by patients and families rather than "health system-centric" barriers. Aim 3 will test the effectiveness of a nurse home visit intervention in improving post-discharge outcomes, including those identified by families in Aim 1, for children hospitalized with acute illness. Aim 4 will test the effectiveness of nurse-led phone call in improving post-discharge outcomes, including those identified by families in Aim 1, for children hospitalized with acute illness. Post-hoc analysis Qualitative analysis: We will use engagement interviews to provide a comprehensive understanding regarding the results of Aim 3. Aim 3 results were unanticipated with those patients receiving the intervention having a higher odds of unscheduled revisits. There are a number of possible reasons for these results. This could reflect greater access to care or improved parental engagement in their child's health. Alternatively, this could reflect unwarranted healthcare utilization as a result of the intervention. Therefore it is imperative to conduct interviews and focus groups to further understand our results. Readmission analysis: In Aim 3, we found patients randomized to the intervention had more post-discharge healthcare utilization. This was driven, in part, due to an increase in 30 day readmissions. Understanding if the readmissions were necessary or preventable is important in understanding our Aim 3 findings. As part of ongoing hospital improvement work, teams of nurses and physicians review 30 day readmissions on a unit-basis (for example, the medical director and nurses from A6 review all readmissions to that unit). The readmission team assesses if the readmission was necessary or avoidable. We will request the results of these reviews for Aim 3 enrolled patients who were readmitted.

BACKGROUND

Transition from hospital to home

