Review of all readmissions occur at the unit level lead by physicians and nurses on the units. We will request information regarding the review of the readmissions including assessment of preventability or possibility of avoiding the readmission. If there are any readmissions to the units which were not reviewed, we would ask the readmission team to please review the case as they normally would. If they are unable to complete the standard readmission review, the assessment of preventability would be missing in our study. We will compare the percentage of readmissions designated as potentially preventable in those patients randomized to the intervention in Aim 3 compared to the percentage of readmissions designated as potentially preventable in those patients randomized to the control group in Aim 3.

DURATION

We expect the consent process for **Aim 1** to take approximately 30 minutes, and the focus groups will be 90 minutes in duration. The nurse home visits in **Aim 2** range from 30-90 minutes, and we expect the follow-up phone call to take no longer than 15 minutes. We expect the follow-up calls to confirm return visits to primary care to take no longer than 15 minutes. We expect the consent process and initial survey for **Aim 3** to take approximately 30 minutes, with the intervention group receiving the 30-90 minute home visit or phone call, and all groups receiving the follow-up phone call which should take no longer than 15 minutes. We expect the consent process and initial survey for **Aim 4** to take approximately 30 minutes, with the intervention group receiving the 15-45 minute nurse phone call, and all groups receiving the follow-up phone call which should take no longer than 15 minutes. The interviews and focus groups in the **Post-hoc analysis** will last 60 minutes or less.

Data analysis will take place sequentially by Aim, and we expect to have initial manuscripts and dissemination plans completed by April 2017. However, it is likely that manuscripts will continue to be written into 2017. Due to the post-hoc analysis, we are extending the completion of final data analysis and dissemination plans to September 2017.

Timeline

SELECTION & RECRUITMENT OF PARTICIPANTS

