Qualitative Analysis: All patients, families, and care providers that meet the above inclusion and exclusion criteria will be eligible for the study. We anticipate enrolling up to 20 participants from each of the following groups: 1) parents of currently admitted patients 2) parents of children previously enrolled in Aim 3 intervention arm 3) parents of children previously enrolled in Aim 3 control arm 4) primary care providers 5) inpatient attending physicians 6) bedside nurses 7) homecare nurses.

Readmission Analysis: We will include all patients enrolled in Aim 3 who were readmitted to CCHMC within 30 days of their initial hospitalization.

PROCESS OF OBTAINING CONSENT

Aim 1

Research personnel will approach families during the hospital stay, provide study information, obtain written consent, and schedule focus group participation. Families will have as much time as they need to consider enrollment in the study during their stay in the hospital. Families will be given time to read the consent forms, and study staff will also verbally go through the forms and allow families to ask questions. For patients at Liberty, we will call them to discuss the consent document over the phone. If they agree to participate, we will have them sign the consent when they arrive for the focus group.

Aim 2

As Aim 2 is based in Quality Improvement Methods, families will not be consented during this Aim. They are free to choose to receive the home visit or not, and study personnel will not contact the families while they are admitted. However, families that receive a follow-up phone call after their home visit will be asked to give verbal consent over the phone prior to completion of the survey.

In order to confirm parent recall of return visits to primary care 30-days after discharge, we will attempt to contact families eligible during Aim 2 who receive primary care at CCHMC for a short follow-up call. We will also confirm their return visits to primary care by reviewing their electronic medical record. We are requesting a waiver of consent for this review as we believe that making the request to review the record during the phone call will bias our results.

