Working hypothesis 2: Patients who receive the nurse home visit intervention will have significantly higher parent activation scores 14-days post-discharge when compared to the patients enrolled in the control group after 14 days post-discharge. For this secondary outcome, the dependent variable will be a continuous measure of parent activation. Difference in this outcome between intervention and control groups will be evaluated using one-way analysis of variance (ANOVA) using a linear model containing a treatment effect indicator. Parental activation scores will be checked for normality and data transformations will be entertained, if needed. Baseline differences will be examined between groups, again using a linear model. If, by random chance, there is a difference between the groups, the first analysis will be repeated but adding the baseline as a covariate.

The sample size was determined based on the comparisons between the control group (standard-of-care) and intervention group (nurse home visit) for the primary outcome measure, a dichotomized indicator of all cause reutilization (i.e., rehospitalization, ED revisit, or unscheduled follow-up) within 30-days post-discharge, and the secondary outcome measure, parent activation score. A sample size of **1500** patients and their families (600 standard-of-care and 600 nurse home visits) was chosen to balance precision and feasibility. Assuming the control group primary outcome rate is 0.20, this sample size allows detectable differences of 0.07 or more (a 35% reduction or more from the control group rate) with 80% power. This detectable difference is lower than differences found in prior studies of adults. The estimated utilization rate of 0.20 in the control group is based on CCHMC data that indicates hospitalist service readmission rates of 5% on the general service and 15% on the surgical service, a 10% ED revisit rate, and a 4% outpatient service utilization rate; we assume that 10% of enrolled patients will come from the surgical service.

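### The Aim 3 readmission analysis compares arms only on percent preventable among readmissions, a post-randomisation denominator; preventable and non-preventable readmission per randomised child should be the main comparison

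*Protocol*

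**What the plan says.** The protocol describes the analysis twice, under Readmission Analysis in STUDY DESIGN and again in DATA ANALYSIS/METHODS. Both define the same contrast: "We will compare the percentage of readmissions designated as potentially preventable in those patients randomized to the intervention in Aim 3", set against the "percentage of readmissions designated as potentially preventable in those patients randomized to the control group in Aim 3". The analysis set is given under SELECTION & RECRUITMENT OF PARTICIPANTS: "We will include all patients enrolled in Aim 3 who were readmitted to CCHMC within 30 days of their initial hospitalization".

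PURPOSE OF STUDY gives the reason for it. In Aim 3, "we found patients randomized to the intervention had more post-discharge healthcare utilization", and "This was driven, in part, due to an increase in 30 day readmissions". It adds: "Understanding if the readmissions were necessary or preventable is important in understanding our Aim 3 findings".

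Preventability is judged by the hospital's unit-level readmission teams. If a team cannot complete its usual review, "the assessment of preventability would be missing in our study". No analysis of those missing reviews is described.

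Neither document adds a comparison per randomised child, a model, a test, or a caution about restricting the comparison to readmissions. The SAP covers Aim 4 and does not contain this analysis.

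**The concern.** Randomisation makes the two arms comparable as randomised. It does not make the readmitted subsets comparable once the intervention has changed who is readmitted, and the protocol itself reports that readmissions rose. Some readmitted intervention children may be children who would have stayed at home under standard care.

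There is also a mismatch with the question. The Aim 3 finding to be explained is an excess per randomised child. Explaining it means splitting that excess into a preventable and a non-preventable part, each with randomised children as the denominator. A percentage within readmissions divides out the very excess under study.

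At stake is how an unexpected result against the intervention is interpreted. A lower percentage in the intervention arm could be taken as reassurance that the extra readmissions were necessary, when preventable readmissions per child had also gone up.

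**Working it through.** **Inputs from the protocol (DATA ANALYSIS/METHODS, Aim 3).** The planning rates are "hospitalist service readmission rates of 5% on the general service and 15% on the surgical service", a 10% surgical share, a 10% ED revisit rate, a 4% outpatient rate and a control composite of 0.20. The sample-size text gives 600 per arm but a total of 1500, so I use 600 to 750 per arm. That mismatch is a separate matter.

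**Assumed, because the documents do not give them.** The readmission ratio between arms and the preventable share in each arm. The illustrations also take each child as readmitted at most once.

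**Reproducing the plan's figure.** No power or expected percentage is stated for the readmission analysis. The rate it rests on can be checked: 0.9 × 5% + 0.1 × 15% = 6.0%, and 6% + 10% + 4% = 20%, which agrees with the stated 0.20. Expected control readmissions are 600 × 0.06 = 36 to 750 × 0.06 = 45.

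**When the two contrasts disagree.** Let R be the readmission rate and p the preventable share, with subscripts I (intervention) and C (control). Preventable readmission per randomised child is R × p. The planned contrast is p_I − p_C; the per-child contrast is R_I p_I − R_C p_C. With R_I > R_C, the first is negative and the second positive exactly when

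R_C/R_I < p_I/p_C < 1.

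The lower limit is 0.91 for a readmission ratio of 1.1, 0.80 for 1.25, 0.67 for 1.5 and 0.50 for 2.0.

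**Illustration: R_C = 6%, ratio 1.5 (R_I = 9%), p_C = 30%.** Control risks per child are 6% × 0.30 = 1.80% preventable and 6% × 0.70 = 4.20% non-preventable.

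| p_I | Planned contrast (points) | Preventable per child, intervention | Change (points) | Non-preventable per child, intervention | Change (points) |
|---|---|---|---|---|---|
| 30% | 0 | 9% × 0.30 = 2.70% | +0.90 | 6.30% | +2.10 |
| 25% | −5 | 9% × 0.25 = 2.25% | +0.45 | 6.75% | +2.55 |
| 20% | −10 | 9% × 0.20 = 1.80% | 0 | 7.20% | +3.00 |
| 15% | −15 | 9% × 0.15 = 1.35% | −0.45 | 7.65% | +3.45 |

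The 25% row arises if the extra readmissions are half as likely to be preventable as the control ones: with 600 per arm, (36 × 0.30 + 18 × 0.15)/54 = 13.5/54 = 25%. The 20% row arises if every extra readmission is non-preventable: 10.8/54 = 20%.

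**Range.** Keep the half-as-likely assumption and vary the ratio from 1.1 to 2.0 and the control share from 10% to 50%. The share falls and the per-child risk rises in every case. At one end (ratio 1.1, share 10%) the share goes from 10% to 9.5% and the risk from 0.60% to 0.63%. At the other (ratio 2.0, share 50%) the share goes from 50% to 37.5% and the risk from 3.00% to 4.50%.

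**Precision.** The planned comparison has little power (two-sided 5%; 36 to 45 control readmissions; ratio 1.25 to 1.5): 18% to 23% for 30% against 20%, and 45% to 57% for 50% against 30%. The per-child contrast is imprecise too. For 1.80% against 2.25% with 600 per arm, the standard error is √[(0.018 × 0.982 + 0.0225 × 0.9775)/600] = 0.81 points, so the 95% interval is 0.45 ± 1.59, about −1.1 to +2.0 points.

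**The case against.** **The percentage answers the question asked.** Whether readmissions were necessary or preventable can be read as a question about their mix, and a lower share does show that the net extra readmissions were less often preventable than the control ones. That stands, and it is why the percentage should be kept. But the share alone does not separate the last three rows of the table, where preventable readmissions per child rise, stay level or fall.

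**The per-child figure can be recovered.** Aim 3 readmission results exist, and rate times share roughly gives preventable risk per child (exactly so if no child is readmitted twice). This also stands. The information is not lost; the plan simply never makes it an output, gives it no interval, and leaves a within-readmission contrast as the only between-arm comparison.

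**The sizes are assumed.** Correct. The protocol gives the direction of the readmission difference but no count, ratio, confidence interval or p value, and no preventable share. A reader might infer that the planned analysis will point the wrong way, or that the intervention caused more preventable readmissions. The documents support neither: disagreement needs the share ratio to fall in a limited window, and nothing shows that it does.

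**It is peripheral.** The analysis is labelled post hoc, has no stated test, concerns Aim 3 rather than the Aim 4 trial covered by the SAP, and may already be finished, since the protocol places final data analysis in September 2017. No primary or secondary conclusion rests on it. This lowers the stakes. Even so, the protocol calls the question important for understanding the Aim 3 result.

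**Conclusion.** The concern holds in a limited form. The sole planned between-arm comparison is conditional on readmission, an event that the protocol reports as more frequent in the intervention arm. It therefore lacks the protection of randomisation and does not by itself apportion the excess per randomised child. As a description of the mix in each arm it is legitimate.

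Disagreement in sign is possible whenever p_I/p_C lies between R_C/R_I and 1. Its size cannot be determined from the documents. In the illustration, a share 5 points lower accompanies a preventable risk 0.45 points higher per child, resting on the implied 6% control rate, the assumed ratio of 1.5 and the assumed shares. Events are few on either denominator, so the result will be imprecise whichever is used. The change is worth making because it matches the analysis to its purpose, not because the planned percentage is shown to mislead.

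**What to change.** 1. Make the main between-arm comparison the proportion of all randomised Aim 3 patients with at least one preventable CCHMC readmission within 30 days and, separately, the proportion with at least one non-preventable one. A child with both counts in both outcomes, which also settles repeat readmissions.
2. Use the Aim 3 logistic model with its stratification factors (chronic condition; general or surgical service). Report differences in proportion with confidence intervals, obtained from the model's predicted risks.
3. Keep percent preventable among readmissions by arm, labelled as descriptive.
4. Report by arm the readmissions without a preventability judgement. Include non-CCHMC readmissions seen in HealthBridge, which the CCHMC review does not reach and which would otherwise count silently as no event. Give bounds counting all or none of them as preventable. Counting all in one arm and none in the other gives the widest bounds.

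**Cost.** No new data collection: the reviews, the HealthBridge records and the randomised denominators are already within the plan. There is slightly more analysis work. Intervals will be wide, with about 36 to 45 control readmissions expected if the 6% rate holds with 600 to 750 per arm. If the analysis is already complete, the same results can be added to its report as a further table.
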